5.2 PARTICIPANT EXCLUSION CRITERIA

- 1. Kidney or other solid organ or bone marrow transplant recipient
- 2. Allergy or intolerance to investigational agent
- 3. Secondary FSGS
- 4. Severe obesity, i.e., BMI >40 kg/m²
- 5. Live virus vaccine in the past 3 months
- 6. Malignancy, current or in the past 5 years
- 7. Active local or systemic bacterial, fungal or viral infection
- 8. Active or latent Hepatitis B, Hepatitis C, HIV, or tuberculosis defined as quantiferon test positive
- 9. History of demyelinating disease, e.g. Multiple Sclerosis or Guillain-Barre
- 10. History of heart failure
- 11. Active liver disease, defined as AST or ALT > 2.5x Upper Limit of Normal
- 12. Systemic lupus erythematosus or ANA > 1:80
- 13. History of inflammatory bowel disease, e.g. ulcerative colitis or Crohns disease
- 14. Cyclophosphamide in past 90 days, Rituximab in the past 180 days
- 15. Pregnancy or nursing

- 16. Blood white blood cell count <4,500/mm3; Hg <9 g/dL; Platelet count <150,000/mm3 at enrollment. Use of an erythropoiesis stimulating agent will not be an exclusion criterion.
- 17. Concurrent use of interleukin-1 antagonist (Anakinra), other TNF blocking agent, methotrexate or abatacept
- 18. Diabetic nephropathy

5.3 STRATEGIES FOR RECRUITMENT AND RETENTION

Patients will be recruited from the active population of patients with FSGS or TR-MCD w at participating sites. TR-MCD is defined as persistent proteinuria despite treatment. Following informed consent and when appropriate, assent, a screening visit will be conducted. Patients with elevated TIMP1/Cr and MCP1/Cr levels and meeting all other eligibility criteria will be scheduled to receive adalimumab every two weeks for 8 weeks (5 total doses). It is anticipated that only 25% of screened patients will be eligible for study participation based on TIMP1/Cr and MCP1/Cr levels. Eight eligible patients will begin study intervention with a goal to have a minimum of 6 patients fully completing the intervention phase and therefore contributing to the final analysis of the primary endpoint after 5 doses of adalimumab over an 8 week period.

Patients will be compensated for study participation to offset costs related to travel to study visits and incidentals.

5.4 PARTICIPANT WITHDRAWAL OR TERMINATION

5.4.1 Reasons for Withdrawal or Termination

Patients participating in this study may withdraw or be terminated for the following anticipated reasons.

- Ongoing participation in this research study is voluntary and patients may leave at any time without an identified cause or the need for explanation.
- Patients experiencing any clinical adverse event (AE), laboratory abnormality, or other medical condition or situation such that continued participation in the study would not be in the best interest of the participant (as determined by the patient and/or study physician).
- Pregnancy and/or breast feeding
- Absolute contraindications to continued therapy with Humira.

5.4.2 HANDLING OF PARTICIPANT WITHDRAWALS OR TERMINATION

Should a participant prematurely withdraw or be withdrawn from the study for any reason, he/she will be asked to return for key outcome determinations at study week 10 and final safety assessment at study week 14. At the week 10 visit any medication prescribed by their treating physician since leaving the study will be recorded, in addition to other required assessments. The participant's reason for withdrawal and their status at the time of withdrawal will be recorded. Should the participant die, the cause of death will be determined and recorded, if possible. This additional data will be utilized in the statistical analysis of the primary and secondary study outcomes as defined by the statistical plan.

5.5 PREMATURE TERMINATION OR SUSPENSION OF STUDY

The investigators and/or other regulatory bodies reserve the right to terminate the study at any time. If this becomes necessary, appropriate procedures for continuing long-term follow-up and assuring the

adequate treatment and safety of the participating subjects will be arranged after review and approval by the Institutional Review Boards.

The DSMB will also provide external oversight concerning the safety and scientific integrity of the study for the duration of the clinical trial. The DSMB will review the progress of the study toward meeting enrollment goals, adverse and serious adverse event profiles, at regular intervals to occur at least twice annually. The DSMB may recommend at any time that the study should be terminated due to drug toxicity, patient safety, poor compliance and/or futility considerations. In such cases, their recommendations will be reviewed and discussed with the Executive Committee, which will make a final determination.

6 STUDY AGENT

6.1 STUDY AGENT(S) AND CONTROL DESCRIPTION

6.1.1 ACQUISITION

Each site will be responsible for acquiring and distributing Humira to the study participants in accordance with all local institutional policies governing the prescription of drugs for research purposes.

6.1.2 FORMULATION, APPEARANCE, PACKAGING, AND LABELING

Humira is supplied as a sterile, preservative-free solution of adalimumab for subcutaneous administration. The drug product is supplied as either a single-use, prefilled pen (Humira Pen), as a single-use, 1 mL prefilled glass syringe, or as a single-use institutional use vial. Enclosed within the pen is a single-use, 1 mL prefilled glass syringe. The solution of Humira is clear and colorless, with a pH of about 5.2.

Formulation and Strength: Any of the commercially available Humira formulations may be used in this study:

- Each 40 mg/0.4 mL prefilled syringe or prefilled pen delivers 0.4 mL (40 mg) of drug product.
- Each 40 mg/0.8 mL prefilled syringe or prefilled pen delivers 0.8 mL (40 mg) of drug product.
- Each 20 mg/0.2 mL prefilled syringe delivers 0.2 mL (20 mg) of drug product.
- Each 20 mg/0.4 mL prefilled syringe delivers 0.4 mL (20 mg) of drug product.

Labeling On-site: At the Clinical Site Research Pharmacy, patient specific labeling will be applied to Humira as this study drug will be provided in an open-label format to study participants. In addition to patient specific labeling information, the drug name, concentration, and date of preparation will be on the label prior to distribution. In accordance with §312.6 the drug will also contain a label with the statement "Caution: New Drug – Limited by Federal (or United States) law to investigational use."

6.1.3 PRODUCT STORAGE AND STABILITY

Humira must be refrigerated at 36°F to 46°F (2°C to 8°C). DO NOT FREEZE. Do not use if frozen even if it has been thawed. Store in original carton until time of administration to protect from light. If needed, for example when traveling, Humira may be stored at room temperature up to a maximum of 77°F

(25°C) for a period of up to 14 days, with protection from light. Humira should be discarded if not used within the 14-day period. Do not use beyond the expiration date on the container. Record the date when Humira is first removed from the refrigerator in the spaces provided on the carton and dose tray. Do not store Humira in extreme heat or cold.

6.1.4 DOSING

Humira will be dosed based on weight at study weeks 0, 2, 4, 6, and 8. This dose has been selected in accordance with the recommended dose of Humira for patients 2 years of age and older with polyarticular juvenile idiopathic arthritis.

Subject Weight	Humira dose (every other week)		
15kg to <30kg	20mg		
≥30kg	40mg		

6.1.5 ROUTE OF ADMINISTRATION

Humira will be given subcutaneously at every other week for 8 weeks (5 total doses).

6.1.6 DOSE ADJUSTMENTS/MODIFICATIONS/DELAYS

If there is evidence of toxicity in abnormal laboratory tests or clinical adverse events that, in the judgment of the Investigator, could place the subject at increased risk, study drug administration should be interrupted and the investigator should notify the trial principal investigator at University of Michigan. Subjects may be considered eligible to receive further study medication treatment only after discussion with the study principal investigator at the University of Michigan.

6.1.7 DURATION OF THERAPY

The total duration of therapy will be 8 weeks with a single dose study drug given subcutaneously at study weeks 0, 2, 4, 6, and 8.

6.2 STUDY AGENT ACCOUNTABILITY PROCEDURES

6.2.1 RESPONSIBILITIES OF THE CLINICAL SITE PHARMACY

The dispensing pharmacy at each site will maintain an independent drug accountability log for all Humira that is dispensed for this study. The log must include at a minimum: the date dispensed, drug expiration date, lot number or other identifying number, and study participant receiving the drug.

6.2.2 THE SITE INVESTIGATOR RESPONSIBILITY

The site team will maintain a drug accountability log for each study patient to document subject number, visit number, date medication dispensed, and date medication returned. Any unused medication should be returned to the study site, documented, and disposed of in accordance with local policy.

7 STUDY PROCEDURES AND SCHEDULE

7.1 STUDY PROCEDURES/EVALUATIONS

Biopsy report: The biopsy report from the qualifying kidney biopsy will have personal identifiers redacted, labeled with the study identification number and then submitted into the study database for review and confirmation of eligible pathology of FSGS or MCD.

Archived Kidney Biopsy Tissue: 4 unstained slides from archived paraffin block kidney tissue will be submitted for gene expression profiling when available. Patients who have submitted tissue from a kidney biopsy as part of NEPTUNE study participation will not be required to have additional tissue submitted as part of this study.

Health Related Quality of Life (HRQOL): The FSGS-MCD Patient Reported Outcome (PRO) assessment will be assessed in accordance with the schedule of events table (7.2.5). The FSGS-MCD PRO assessment should be completed by the participant at each in-person study visit.

Adverse events: Adverse event assessments will be done at each study visit as detailed in Section 9. Complete medical history: The complete medical history will include a review of pertinent medical records covering details related to the patient's history of FSGS or TR-MCD provided by the patient and/or their referring physician(s).

Physical examination: A physical exam will include a review of systems and current physical findings Interval medical history: A review of medications, interval symptoms, and any changes to the patient's medical history will be reviewed and documented.

Vital signs: Vital signs will include: blood pressure, temperature (°C), height (cm), and weight (kg) will be measured.

Pregnancy Testing: For study participants of child-bearing potential, a urine pregnancy test will be performed at screening and each study visit prior to adalimumab administration.

Clinical Laboratories: A comprehensive set of laboratory results will be performed on blood and urine samples to evaluate any toxicity or adverse events associated with FSGS or TR-MCD or its treatment with the study drug.

- Comprehensive metabolic panel (Comp): including serum electrolytes, BUN, creatinine, glucose, albumin, ALT, AST, alkaline phosphatase, total bilirubin, cholesterol, total protein
- Complete blood count with differential (CBCD): including WBC, hemoglobin, hematocrit, platelet count, and differential cell count.
- **Urine protein/creatinine ratio:** 24-hour urine collection preferred, but first morning urine or spot urine is acceptable

Assessment of Infections:

- Hepatitis B: HBsAg, HBcAb IgG testing will be conducted at screening for all potentially eligible
 participants unless hepatitis screening has been conducted clinically within the past 45 days
 with documentation of results.
- Hepatitis C: HCAb screen will be conducted at screening for all potentially eligible participants
 unless hepatitis screening has been conducted clinically within the past 45 days with
 documentation of results.
- HIV -1/HIV-2 antibody differentiation immunoassay will be conducted at screening for all
 potentially eligible participants unless HIV screening has been conducted clinically within the
 past 45 days with documentation of results.
- **Tuberculosis:** Quantiferon for tuberculosis should be measured unless tuberculosis screening has been conducted clinically within the past 45 days with documentation of results.

Serology:

• Antinuclear cytoplasmic autoantibody (ANA): should be measured at screening unless conducted clinically within the past 45 days with documentation of results.

Urine collection for target engagement biomarkers: A spot urine sample will be collected at each in person study visit before the administration of the study drug.

Optional Biological Specimen Repository: 10ml of Blood (serum, plasma, RNA and DNA (8.5 ml at the screening visit only)) and urine samples will be collected at each study visit for storage at the University of Michigan Biorepository. The specimens will be made available for approved investigations for future kidney disease related research.

Study drug reconciliation: Document subject number, visit number, date medication dispensed, and lot number at each visit in accordance with section 6.2.

Study drug administration: At week 0 the study team will administer Humira to the subject, and monitor the subject for 15 minutes post injection, recording blood pressure and heart rate at 15 minutes post injection. Subject/guardian will be taught how to administer Humira to themselves or their child. At week 2, the subject/guardian should administer Humira while study staff observes to ensure proper technique. An ice pack may be applied to the injection site to alleviate pain associated with the injection as needed.

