2.3 POTENTIAL RISKS AND BENEFITS

2.3.1 KNOWN POTENTIAL RISKS

SERIOUS INFECTIONS

Some patients treated with Humira (adalimumab) are at increased risk for developing serious infections that may lead to hospitalization or death. Most patients who developed these infections were taking concomitant immunosuppressants such as methotrexate or corticosteroids.

Reported infections include:

Active tuberculosis (TB), including reactivation of latent TB. Patients with TB have frequently presented with disseminated or extrapulmonary disease. Study participants will be tested for TB before starting Humira.

Invasive fungal infections, including histoplasmosis, coccidioidomycosis, candidiasis, aspergillosis, blastomycosis, and pneumocystosis. Patients with histoplasmosis or other invasive fungal infections may present with disseminated, rather than localized, disease. Antigen and antibody testing for histoplasmosis may be negative in some patients with active infection. Consider empiric anti-fungal therapy in patients at risk for invasive fungal infections who develop severe systemic illness. Bacterial, viral, and other infections due to opportunistic pathogens, including Legionella and Listeria.

MALIGNANCIES

Lymphoma and other malignancies, some fatal, have been reported in children and adolescent patients treated with TNF blockers, including Humira. Postmarketing cases of hepatosplenic T-cell lymphoma (HSTCL), a rare type of T-cell lymphoma, have been reported in patients treated with TNF blockers, including Humira. These cases have had a very aggressive disease course and have been fatal. The majority of reported TNF blocker cases have occurred in patients with Crohn's disease or ulcerative colitis and the majority were in adolescent and young adult males. Almost all of these patients had received treatment with azathioprine or 6-mercaptopurine concomitantly with a TNF blocker at or prior to diagnosis. It is uncertain whether the occurrence of HSTCL is related to use of a TNF blocker or a TNF blocker in combination with these other immunosuppressants.

HYPERSENSITIVITY

Anaphylaxis and angioneurotic edema have been reported following Humira administration. If a serious allergic reaction occurs, stop Humira and institute appropriate therapy.

HEPATITIS B VIRUS REACTIVATION

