Use of TNF blockers, including Humira, may increase the risk of reactivation of hepatitis B virus (HBV) in patients who are chronic carriers. Some cases have been fatal. Study participants will be screened for HBV. Those with prior evidence of HBV infection will not be allowed to participate in this study.

NEUROLOGIC REACTIONS

TNF blockers, including Humira, have been associated with rare cases of new onset or exacerbation of central nervous system and peripheral demyelinating diseases, including multiple sclerosis, optic neuritis, and Guillain-Barré syndrome. Participants with these disorders will be excluded from the study. If any of these disorders develop, Humira will be discontinued.

HEMATOLOGIC REACTIONS

Rare reports of pancytopenia, including aplastic anemia, have been reported with TNF blockers. Medically significant cytopenia has been infrequently reported with Humira.

CONGESTIVE HEART FAILURE

Worsening and new onset congestive heart failure (CHF) has been reported with TNF blockers. Cases of worsening CHF have been observed with Humira. Participants with known CHF will be excluded from the study.

AUTOIMMUNITY

Treatment with Humira may result in the formation of autoantibodies and, rarely, in development of a lupus-like syndrome. Discontinue treatment if symptoms of a lupus-like syndrome develop.

IMMUNIZATIONS

Patients on Humira should not receive live vaccines. Pediatric patients, if possible, should be brought up to date with all immunizations before initiating Humira therapy. Adalimumab is actively transferred across the placenta during the third trimester of pregnancy and may affect immune response in the in utero exposed infant. The safety of administering live or live-attenuated vaccines in infants exposed to Humira in utero is unknown. Risks and benefits should be considered prior to vaccinating (live or live-attenuated) exposed infants.

ADVERSE REACTIONS

The most common adverse reactions in Humira clinical trials (>10%) were: infections (e.g., upper respiratory, sinusitis), injection site reactions, headache, and rash.

Directly relevant to this protocol, two small studies of TNF-inhibition with monoclonal antibody therapy in children and adults with multi-drug resistant FSGS have been reported.

•	•
Event	Frequency (% of patients reporting)
Severe Adverse Events	
Infection with hospitalization	30% (5/17)
Malignancy	0
Death	0
Other Adverse Events	
GI	24% (4/17)

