7.3 JUSTIFICATION FOR SENSITIVE PROCEDURES

HIV, hepatitis B and hepatitis C testing is a part of the screening procedures as therapy with adalimumab is contraindicated for persons with active infections. Should HIV, hepatitis B, hepatitis C or tuberculosis/quantiferon testing be positive, the patient will be referred for clinical care through local treatment experts according to local standards of care and excluded from the study.

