APPENDIX

A. Humira Product Information

HIGHLIGHTS OF PRESCRIBING INFORMATION

These highlights do not include all the information needed to use HUMIRA safely and effectively. See full prescribing information for HUMIRA

HUMIRA (adalimumab) Injection, Solution for Subcutaneous use Initial U.S. Approval: 2002

WARNING: RISK OF SERIOUS INFECTIONS

See full prescribing information for complete boxed warning.
Tuberculosis (TB), invasive fungal, and other opportunistic infections, some fatal, have occurred in patients treated with HUMIRA. Perform test for latent TB; if positive, start treatment for TB prior to starting HUMIRA. Monitor all patients for active TB during treatment, even if initial latent TB test is negative (5.1)

RECENT MAJOR CHANGES -

Indications and Usage, Crohn's Disease (1.4)	2/2007			
Indications and Usage, Plaque Psoriasis (1.5)	1/2008			
Dosage and Administration, Crohn's Disease (2.2)	7/2007			
Dosage and Administration, Plaque Psoriasis (2.3)	1/2008			
Warnings and Procautions, Serious Infections (5.1)	2/2007			
Warnings and Precautions, Malignancies (5.2)	1/2008			
Warnings and Precautions, Immunizations (5.10)	2/2007			

HUMIRA is a tumor necrosis factor (TNF) blocker indicated for treatment of: Rheumatoid Arthritis (RA) (1.1)

- Reducing signs and symptoms, inducing major clinical response, inhibiting the progression of structural damage, and improving physical function in adult patients with moderately to severely active disease.
 Psoriatic Arthritis (1.2)
- Reducing signs and symptoms of active arthritis, inhibiting the progression of structural damage, and improving physical function.
 Anhydroine Spondwhits (1.3)
- Ankylosing Spondylitis (1.3)

 Reducing signs and symptoms in patients with active disease.

 Crohn's Disease (1.4)
- Reducing signs and symptoms and inducing and maintaining clinical remission in adult patients with moderately to severely active Crohn's disease who have had an imadequate response to conventional therapy.
 Reducing signs and symptoms and inducing clinical remission in these patients if they have also lost response to or are intolerant to infliximab.
 Plaque Psoriasis (1.5)
- The treatment of adult patients with moderate to severe chronic plaque psoriasis who are candidates for systemic therapy or phototherapy, and when other systemic therapies are medically less appropriate.

----- DOSAGE AND ADMINISTRATION ----

HUMIRA is administered by subcutaneous injection.

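### The 45-day waivers for tuberculosis and hepatitis B testing in Protocol 7.1 do not require that the earlier screen used the tests named there

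*Protocol*

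**What the plan says.** Protocol 7.1, under Assessment of Infections, sets the pre-treatment infection tests and lets each be skipped if earlier clinical results exist.

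- **Tuberculosis:** "Quantiferon for tuberculosis should be measured unless tuberculosis screening has been conducted clinically within the past 45 days with documentation of results".
- **Hepatitis B:** the requirement is "HBsAg, HBcAb IgG testing will be conducted at screening for all potentially eligible" participants, with the waiver "unless hepatitis screening has been conducted clinically within the past 45 days", provided the results are documented.

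The related provisions are:

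- Exclusion 8 in Protocol 5.2, repeated in SAP 5.2.2, bars "Active or latent Hepatitis B, Hepatitis C, HIV, or tuberculosis defined as quantiferon test positive".
- The risk section (2.3.1) says "Study participants will be tested for TB before starting Humira" and, for hepatitis B, "Those with prior evidence of HBV infection will not be allowed to participate in this study".
- The product information in Appendix A says "Perform test for latent TB; if positive, start treatment for TB prior to starting HUMIRA".
- Section 7.3 refers and excludes patients "Should HIV, hepatitis B, hepatitis C or tuberculosis/quantiferon testing be positive".
- Section 7.2.1 deems a patient eligible once screening is complete, all inclusion criteria are met and no exclusion criterion is met.

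**The concern.** Each bullet asks for specific assays, but its waiver is triggered by a broader activity: tuberculosis screening in one case, hepatitis screening in the other. The text does not say that the earlier activity must have included the assays it replaces.

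The protocol handles reactivation of tuberculosis and hepatitis B by testing before the first dose and excluding those affected. Section 2.3.1 records that some hepatitis B reactivations were fatal. It also says that most patients with serious infections on the drug were taking other immunosuppressants, and inclusion criterion 8 allows stable oral immunosuppression. The schedule of events places infection assessment at screening only, so a test waived then is not picked up at a later visit. A site that applies the waiver literally could start adalimumab without the result that 7.1 asks for as the safeguard.

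**Working it through.** There is no figure to reproduce. The check compares each waiver with the tests its bullet names, then looks for other text that would restore the requirement.

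**Step 1: what each waiver refers back to.**

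| Bullet in 7.1 | Test named | What triggers the waiver | Tied to the named test? |
|---|---|---|---|
| Tuberculosis | Quantiferon | clinical tuberculosis screening, 45 days | No |
| Hepatitis B | HBsAg and HBcAb IgG | clinical hepatitis screening, 45 days | No |
| ANA (serology) | ANA | the ANA itself done clinically, 45 days | Yes |

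The ANA line, in the same section, shows a waiver that does refer back to its own test. The hepatitis B waiver does not even specify type B.

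**Step 2: tuberculosis, followed as written.** Take a patient with a documented negative result on some other tuberculosis test within 45 days.

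1. The 7.1 waiver applies, so no Quantiferon is required.
2. Exclusion 8 acts on a positive Quantiferon. It does not ask for a negative one, so with none on file it is not triggered.
3. Section 2.3.1 and Appendix A call for a tuberculosis test without naming one, so another latent-tuberculosis test satisfies both.
4. The patient passes the 7.2.1 gate and can be dosed at week 0.

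The mismatch is therefore with exclusion 8 only. Had the other test been positive, section 7.3 would probably still have excluded the patient.

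**Step 3: hepatitis B, followed as written.** Take a patient with a documented negative HBsAg within 45 days and no core antibody result.

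1. The 7.1 waiver applies, so no HBcAb is required.
2. Exclusion 8 bars active or latent infection but names no hepatitis B test.
3. Section 2.3.1 bars prior infection, again without naming a test.
4. Section 7.3 acts on positive results and cannot act on a test that was not run.
5. The schedule of events lists infection assessment at screening without naming assays.
6. The patient passes the 7.2.1 gate and can be dosed.

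HBcAb is named only in the bullet that can be waived. By asking for both assays, 7.1 itself treats HBsAg alone as not enough.

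**Step 4: size.** The maximum treated is 8 (Protocol 8.5). Neither document says how many patients used a waiver or what their earlier screens contained. The number dosed without a named test therefore lies between 0 and 8, and the documents do not narrow that range.

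**The case against.** The strongest reply is that the waivers are shorthand. The bullet's heading names the infection, its sentence names the tests, and the screening in the waiver means that same screen. The literal reading also leads somewhere odd: the hepatitis B and hepatitis C bullets share the same waiver phrase, so an earlier hepatitis C screen would waive hepatitis B testing, which no site would intend. For tuberculosis, a criterion defined by one assay is most naturally cleared with that assay's result, and the paired wording in 7.3 suggests the protocol treats tuberculosis testing and Quantiferon as one thing. For hepatitis B, the investigator must still judge prior or latent infection, with the medical records in hand. The documents do not say how often clinical screens omit HBcAb, and the SAP suggests that treatment is over.

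Much of this stands. A careful site may well read the waivers as intended, and the tuberculosis half is mainly an inconsistency with exclusion 8. The practical likelihood of either scenario is unknown.

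The wording gap remains. The waiver is an explicit permission to omit the test, and no other section withdraws it. The eligibility gate is judged on the results at hand and does not produce a result that was never obtained. The hepatitis C overlap is a further sign that the phrase is too loose.

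**Conclusion.** The concern holds as a minor safety-wording correction. As written, 7.1 lets a patient be dosed without a Quantiferon result or without an HBcAb result. Hepatitis B is the stronger half, because no other text asks for the core antibody. For tuberculosis the fault is that 7.1 and exclusion 8 disagree about which test decides.

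The conclusion rests on reading the waivers literally. Exposure is at most 8 patients and may be none. No rate of missed infection is claimed, nothing in the documents shows that a patient was dosed wrongly, and no endpoint or analysis is affected.

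**What to change.** Change two waivers in Protocol 7.1:

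- **Tuberculosis:** waive only if a documented Quantiferon result from the past 45 days is available. If another tuberculosis test is acceptable, name it both in the waiver and in exclusion 8 (Protocol 5.2 and SAP 5.2.2).
- **Hepatitis B:** waive only if documented results of both HBsAg and HBcAb IgG from the past 45 days are available.

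The hepatitis C and HIV waivers have the same form and could be tightened in the same edit, although this point does not depend on them.

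SAP 1.1 describes treatment in the past tense. If dosing is complete, check the screening records of the treated patients, at most 8, for the named results, and use the corrected wording in any later protocol that reuses this text.

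The cost is a few words and that short record check. In a trial still enrolling, the downside is an occasional repeat assay on the screening blood draw for a patient whose earlier screen was different or incomplete.
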